6.5. Missing Data

The primary analytical method for most of the study's efficacy objectives is a time-to-event analysis. The methods handle missing or unobserved data by classifying each subject's event as censored at the time of the

first missing result if no events are observed subsequent to that time point. In the case of intermittent missing data, the methods assume no event occurred. Subjects who receive treatment for incident HCV infection will be censored from time to event analyses of chronic infection at the date of first treatment.

No other imputation of missing data is planned.

6.6. Interim Analyses and Data Monitoring

Interim analyses are described in separate Interim Analysis and Ongoing Endpoint Assessment Statistical Analysis Plans.

6.7. Multicenter Studies

As described in Section 4.4.3 and Section 6.4, the randomization of treatment assignments and the primary analysis will be performed as stratified by gender and IL28B status. Randomization is also stratified by clinical site, however given that the University of New Mexico was added late in enrollment (first enrollment 16 November 2015); stratifying efficacy analyses by site in addition to gender and IL28B may result in insufficiently sized strata. Thus, efficacy analyses will not be stratified by site.

Though sites are using standardized procedures for vaccination and assessment of solicited and unsolicited adverse events, and the study relies on central laboratories for the assessment of immunogenicity and clinical efficacy endpoints, there is expected variation in the demographics and risk behavior in the patient population between sites, so site effects of safety data are expected. Estimates of site effects should be considered exploratory given that the study was not explicitly designed with enough power to detect site effects.

See Section 9 for descriptions of the by-site analyses for safety analyses.

6.8. Multiple Comparisons/Multiplicity

No adjustments for multiple testing are planned.

7. STUDY SUBJECTS

7.1. Disposition of Subjects

The disposition of subjects in the study will be tabulated by randomized treatment group and for all subjects. [Table 4](#) shows the number of subjects who are screen failures and the number of subjects that met each inclusion/exclusion criterion. [Table 5](#) summarizes the mITT population eligibilities by randomized treatment group and reasons excluded and [Table 6](#) summarizes the safety, ATP and Immunogenicity analysis population eligibilities by actual treatment group and reasons excluded. Subjects will be included in the count for a particular reason for Exclusion if they met that criterion. As subjects may meet more than one criterion for exclusion, the “Excluded from...” counts may be less than the sum of the individual reason counts. A listing of the subjects excluded from each of the analysis populations and the reasons for exclusion will be provided ([Listing 1](#)). The number of enrolled subjects in the study completing study milestones will be tabulated separately by randomized treatment group. [Table 3](#) shows the total number of subjects enrolled, randomized, receiving first vaccination, receiving second vaccination, with and without confirmed HCV infection, terminated from study follow-up, and completing the study by randomized treatment group. A listing of subjects who completed the study, terminated early from study, or discontinued treatment and the reason for early termination or treatment discontinuation is included in [Listing 3](#).

[Figure 2](#) is a flowchart showing the disposition of study subjects in the primary efficacy analysis, adapted from the CONSORT statement. It shows the number of subjects eligible, enrolled and randomized, lost to follow-up, and analyzed for the primary efficacy analysis, overall and by treatment group.

7.2. Protocol Deviations

A summary of subject-specific protocol deviations will be presented by the deviation category, the type of deviation, and randomized treatment group for all enrolled subjects ([Table 7](#)). All subject-specific protocol deviations and non-subject-specific protocol deviations will be included in Appendix 3 as data listings ([Listing 4](#) and [Listing 5](#), respectively).

8. EFFICACY EVALUATION

All efficacy variables will be listed by subject and summarized by analysis population and treatment group. Continuous efficacy variables will use some or all of the following: n, Mean, Standard Deviation, Median, Minimum and Maximum, whereas Number and Percent will summarize categorical efficacy variables. Confidence intervals for binomial proportions and difference in binomial proportions will be computed using the Wilson confidence limits. All analyses of the time-to-event efficacy variables will be performed using Kaplan-Meier or Cox regression methods. Treatment groups will be tested at the 2-sided 5% significance level. All assumptions for regression models will be assessed by viewing plots of the residual values and other diagnostic plots, though these will not be included in the final report.

8.1. Primary Efficacy Analysis

For the evaluation of the primary efficacy objective of this study, a time to event analysis will be performed in the ATP cohort as follows:

- For subjects without HCV infection, the 6-month chronic infection endpoint will be coded as censored, with time to event defined as the elapsed time from the second vaccination, to the end of the 26 months follow up, or to the last observed visit before loss to follow-up or to the earliest time any criterion listed under the censoring criteria for the ATP cohort was met.
- For subjects who develop HCV infection, the 6-month chronic infection endpoint will be coded as an observed event if the 6-month chronic infection endpoint definition is met, and as censored otherwise, with time to event (chronic or non-chronic infection) defined as the elapsed time from the second vaccination to the date of the sample collection with available test result nearest to the target assessment date of six months after incident infection.

Kaplan-Meier curves for chronic HCV infection will be generated for both the ATP and mITT populations (Figure 3 and Figure 4).

As the primary analysis of the primary outcome measure, the reduction in chronic HCV incidence will be calculated from the hazard ratio of a stratified Cox model for the ATP population. The stratification factors that will be used are gender and IL28B status (i.e. there will be four strata: Female & CC, Female & CT/TT, Male & CC, Male & CT/TT). The model to be fit for subject i is:

$$\log h_i(t) = \alpha_j(t) + \beta x_i$$

where $h(t)$ is the hazard function at time t , $\alpha_j(t)$ is the logarithm of the baseline hazard function for strata j , x_i is a binary indicator for membership in the vaccine as compared to the placebo group.

The model described above will be fit and estimates of vaccine efficacy ($1 - \text{Hazard Ratio}$) will be obtained using PROC PHREG following the pseudocode below:

```
proc phreg data=dataset;
model time*status(0) = treatment;
strata gender il28status;
Ods output parameterestimates=ests(keep=HazardRatio HRUpperCL HRLowerCL);
run;
```

Vaccine Efficacy = $1 - \text{Hazardratio}$;

Lower 95% CI = $1 - \text{HRUpperCL}$ which is the same as $1 - \exp(\text{estimate} + \Phi^{-1}(.975) * \text{stderrratio})$

Upper 95% CI= 1 – HRLowerCL which is the same as $1 - \exp(\text{estimate} - \Phi^{-1}(.975) * \text{stderrratio})$

The p-value of the score test of the treatment main effect (equivalent to the log-rank test) will be calculated and presented. The number of 6-month chronic HCV infections per treatment group, the estimated vaccine efficacy and associated 95% confidence interval will be summarized by treatment group in [Table 8](#).

Secondary and sensitivity analyses of the primary efficacy outcome measure will be performed. First, the analysis will be repeated in the mITT cohort as follows:

- For subjects without HCV infection, the 6-month chronic infection endpoint will be coded as censored, with time to event defined as the elapsed time from the first vaccination to the end of the 26 month follow-up, or to the last observed visit before loss to follow-up or of a criterion listed under the censoring criteria for the mITT cohort.
- For subjects who develop HCV infection, the 6-month chronic infection endpoint will be coded as an observed event if the 6-month chronic infection endpoint definition is met, and as censored otherwise, with time to event defined as the elapsed time from the first vaccination to the date of the sample collection with available test result nearest to the target assessment date of six months after primary infection.

The reduction in chronic HCV incidence will be calculated from the hazard ratio of a stratified Cox model for the mITT population as described above ([Table 8](#)). Stratum-specific summaries will be presented in [Table 9](#).

Second, a sensitivity analysis will be performed in which a Cox model will be fit with binary indicators for membership in the vaccine as compared to the placebo group, and including female as compared to male, and CC IL28B status compared to CT/TT as fixed effects in the model rather than stratification factors. The interaction between time and gender will be assessed using the product of time and the binary indicator for gender as an interaction term in the model. Likewise, the interaction between time and IL28B status will be assessed using the product of time and the binary indicator for gender as an interaction term in the model. The interaction estimates will be provided in the report text and not included in a table. The reduction in chronic HCV incidence will be calculated from the hazard ratio of this model.

The model described above will be fit using PROC PHREG following the pseudocode below:

```
proc phreg data=dataset;
model time*status(0) = treatment gender|time il28bstatus|time;
Ods output parameterestimates=ests(keep=HazardRatio HRUpperCL HRLowerCL);
run;
```

The p-value from the score test of the treatment main effect will be calculated and presented. Results of this sensitivity analysis will be provided in [Table 8](#).

Finally, a sensitivity analysis will be performed, in which subjects who develop HCV infection and do not go on to develop chronic infection will be treated as experiencing a competing risk in the Fine-Gray proportional hazards regression model.

Both the stratified and unstratified with interaction terms models will be fit.

```
proc phreg data=dataset;
class treatment / order=internal ref=first param=glm;
model time*status(0) = treatment / eventcode=1;
hazardratio treatment / diff=pairwise;
```

```

strata gender il28bstatus;
Ods output parameterestimates=ests(keep=HazardRatio HRUpperCL HRLowerCL);
run;

proc phreg data=dataset;
class treatment / order=internal ref=first param=glm;
model time*status(0) = treatment gender|time il28bstatus|time /
eventcode=1;
hazardratio treatment / diff=pairwise;
Ods output parameterestimates=ests(keep=HazardRatio HRUpperCL HRLowerCL);
run;

```

The same summaries as the mITT analyses will be calculated and presented. Results of this sensitivity analysis will be provided in [Table 8](#) and [Table 9](#).

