5. SAMPLE SIZE CONSIDERATIONS

Sample size calculations are based on the assumption of detecting a 60% reduction in incidence of chronic infection over 18 months of post-vaccination follow-up among vaccinated subjects compared to unvaccinated controls in an according to protocol (ATP) analysis. A total of 43 observed events of chronic infection in the ATP cohort would provide power of 85% for a two-sided log rank test conducted at the significance level (alpha) of 0.05 to detect a 60% reduction in hazard rate. The incidence of chronic infection among controls is assumed to be 14% annually [10]. Assuming 14 cases/100 person-years (PY) in the control group, and 5.6 cases/100 PY in the vaccine group, a total of 292.5 subjects in the ATP cohort followed for 1.5 years would provide on average 43 events. We further assume that 65% of enrolled subjects will be retained in the ATP cohort. Therefore, we inflate the required number of subjects by a factor of $1/0.65$ and obtain a target enrollment of 540 subjects, or 270 subjects per vaccination group.

The original enrollment target of the study was 344 subjects. At the April 29, 2014 DSMB meeting, the DSMB reviewed the progress towards the goal of 43 observed events of chronic infection in the ATP cohort and recommended increasing the target enrollment from 344 to 450, or 225 subjects per vaccination group.

At the September 2, 2015 DSMB meeting, the DSMB reviewed the progress towards the goal of 43 observed events of chronic infection in the ATP cohort and recommended increasing the target enrollment from 450 to 540 subjects, or 270 subjects per vaccination group.

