- The primary event of interest is chronic HCV with genotype 1 and the competing event is chronic HCV with genotype other than 1.
- The primary event of interest is chronic HCV with genotype other than 1 and the competing event is chronic HCV with genotype 1.

Kaplan-Meier curves will be presented in [Figure 11](#) and [Figure 12](#). Regression model summaries will be presented in [Table 25](#) and [Table 26](#).

Additional Exploratory Analyses

A summary of study rates by treatment group and site are provided in [Table 27](#) and [Table 28](#), respectively.

With regard to the primary efficacy endpoint, as all possible cases, including cases with uncertain classification for chronicity, will be reviewed by a blinded independent endpoint review committee (ERC) to make a determination of infection outcome. This committee will be comprised of the study PIs, HCV experts, and the SDCC. An interim case review committee comprised of HCV experts, the SDCC, and DMID met on October 14, 2016 and the members were concerned that the endpoint definition in the protocol does not account for subjects with mixed genotype infections; so, if a person's dominant genotype changes over the 6-month period, per the protocol, the subject would not be included as a 6-month chronically infected endpoint case but, in practice, the person still has chronic HCV infection. It was proposed that in addition to the "per protocol" assessments, that the ERC voting members provide their "real-world" and "expert clinical" assessment. The Committee asked that an exploratory analysis of 6-month and 9-month chronicity be conducted using their "expert clinical" non-per protocol assessment of chronic infections to include these more complex cases of potential mixed infections and to include subjects who miss the 6-month visit window, but remain viremic afterwards.

At the final ERC review, the committee will determine case status per protocol as well as ERC-defined cases. The number of 6 and 9 month chronic HCV infections as determined by the ERC per treatment group and the vaccine efficacy and associated 95% confidence interval will be summarized by treatment group in [Table 29](#) and [Table 30](#) for the mITT and ATP populations.

Subject listings of HCV infection status and HCV positive quantitative results are provided in [Listing 24](#) and [Listing 25](#), respectively. A listing of genotyping results, sequence evaluation and ERC Assessment is provided in [Listing 26](#).

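### The Kaplan-Meier figures for chronic infection censor events the SAP itself treats as competing, so read as cumulative incidence they are modestly too high

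*SAP*

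**What the plan says.** SAP 8.1 codes a subject who becomes infected as an event if the 6-month chronic definition is met. Otherwise the subject is censored at the sample nearest six months after infection. From that coding, "Kaplan-Meier curves for chronic HCV infection will be generated for both the ATP and mITT populations" (Figures 3 and 4). SAP 8.3 carries the plan over to the 9-month endpoint (Figures 7 and 8).

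The SAP also recognises competing risks. The last sensitivity analysis in 8.1 is a Fine-Gray model in which infection that does not become chronic is the competing risk. For exploratory objective 5, Fine-Gray is the main model: "The primary event of interest is chronic HCV with genotype 1 and the competing event is chronic HCV with genotype other than 1". For that objective too, "Kaplan-Meier curves will be presented in" Figures 11 and 12. The figure list in SAP Appendix 2 contains no cumulative incidence curve.

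The primary estimate is one minus the hazard ratio from a stratified Cox model, with a score (log-rank) p-value.

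**The concern.** Kaplan-Meier treats a censored subject as someone who could still have the event later. A subject who has cleared a primary infection cannot later supply a chronic primary infection. Under Protocol 8.3, infected subjects also leave the study about 270 days after detection. One minus Kaplan-Meier then estimates the risk in a setting where clearance, or the other genotype, does not occur. It is always at least as large as the proportion who actually become chronically infected.

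Figures 3 and 4 are the only planned plots of the primary endpoint by arm, and readers take absolute risks from such plots. The Fine-Gray results in Tables 8, 9, 14, 15, 25 and 26 would have no plot on their own scale. Protocol 2.1 bases efficacy on T-cell responses like those seen in resolving infection, so clearance may well differ by arm.

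**Working it through.** **The plan's own figure.** SAP 5 gives "power of 85% for a two-sided log rank test conducted at the significance level (alpha) of 0.05" with 43 events, for a 60% reduction (hazard ratio 0.40). Schoenfeld's formula: 4 × (1.960 + 1.036)² / (ln 0.40)² = 42.8, rounded up to 43. SAP 5 also states "Assuming 14 cases/100 person-years (PY) in the control group, and 5.6 cases/100 PY in the vaccine group" and "a total of 292.5 subjects in the ATP cohort followed for 1.5 years would provide on average 43 events". Check: 146.25 × 1.5 × (0.14 + 0.056) = 43.0. Both reproduce, so these rates are used below.

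**Inputs**
- Chronic rates: 0.14 (placebo) and 0.056 (vaccine) per year, T = 1.5 years (SAP 5).
- All primary infections, upper value: 0.27 per year (Protocol 11.4.5).
- All primary infections, lower value: Protocol 2.1 says about 20% of acute infections resolve, so 0.14 / 0.8 = 0.175 per year.
- Assumed: constant hazards, and the same infection rate in both arms (vaccine acts only through clearance).

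**Formulas**
- One minus Kaplan-Meier, competing events censored: 1 − exp(−h_chronic × T).
- Cumulative incidence: (h_chronic / h_all) × [1 − exp(−h_all × T)].

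**Kaplan-Meier.** Placebo 1 − exp(−0.21) = 18.94%. Vaccine 1 − exp(−0.084) = 8.06%.

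**Cumulative incidence at 27 per 100 person-years.** Placebo (0.14/0.27) × (1 − exp(−0.405)) = 17.27%. Vaccine (0.056/0.27) × (1 − exp(−0.405)) = 6.91%.

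| Infections per 100 PY | Arm | 1 − KM | Cumulative incidence | Excess, points | Excess, relative |
|---|---|---|---|---|---|
| 27 | Placebo | 18.94% | 17.27% | 1.67 | 9.7% |
| 27 | Vaccine | 8.06% | 6.91% | 1.15 | 16.6% |
| 20 | Placebo | 18.94% | 18.14% | 0.80 | 4.4% |
| 20 | Vaccine | 8.06% | 7.26% | 0.80 | 11.0% |
| 17.5 | Placebo | 18.94% | 18.47% | 0.47 | 2.6% |
| 17.5 | Vaccine | 8.06% | 7.39% | 0.67 | 9.1% |

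A simulation at 27 per 100 person-years (146 per arm, 4,000 runs, event dated six months after infection, with and without 20% yearly dropout) agreed. Kaplan-Meier gave 18.9–19.0% and 8.1%; Aalen-Johansen gave 17.2–17.3% and 6.9%.

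**If the vaccine also prevents infection.** When all of the 60% reduction comes from fewer infections, the vaccine excess falls to 0.30 points (3.9% relative) at 27 per 100 person-years, and to 0.08 points (1.0%) at 17.5. The placebo excess is unchanged. The relative order of the arms reverses once infections fall by about one third (at 27) to one half (at 17.5).

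**Genotype 1 curves, other-genotype chronic infection as the only competing event.** The SAP's hypothesised effects are 75% (genotype 1) and 45% (non-1). The genotype 1 share is assumed to lie between 50% and 88.5%; the upper value is the US share in Protocol 2.1.
- Share 50%: placebo 9.97% against 9.47% (0.50 points, 5.2% relative); vaccine 2.59% against 2.52% (0.07 points, 2.9%).
- Share 88.5%: placebo 16.96% against 16.76% (0.20 points, 1.2%); vaccine 4.54% against 4.51% (0.03 points, 0.7%).

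If cleared infections are censored in these curves as well (27 per 100 person-years, no effect on infection), the relative excess is 11.0–15.4% in placebo and 18.8–20.0% in vaccine.

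**The case against.** The strongest reply is that nothing inferential changes. Vaccine efficacy comes from a cause-specific Cox model, and a Kaplan-Meier plot with the same censoring is its usual companion. Incidence is also reported as counts in Table 8 and per 100 person-years in Tables 27 and 28, and Fine-Gray models are already planned. All of this stands, and it makes the point one of presentation. The excess is also small beside sampling error: with about 146 per arm, the standard error of the placebo estimate is about √(0.173 × 0.827 / 146) = 3 points. But that error is random, whereas the excess always runs in one direction and can be avoided.

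Two stronger readings are tempting, and the documents support neither.

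- *The vaccine arm is distorted more.* This holds in relative terms if the vaccine works mainly by clearance. In absolute points placebo is affected more at 27 infections per 100 person-years, and the arms are equal at 20. For other-genotype events alone, placebo is affected more on both scales. The error in the gap between the curves has no fixed sign either: 10.9 against 10.4 points at 27, and 10.9 against 11.1 at 17.5.
- *The curves understate efficacy, at 57% instead of 60%.* The 57% is 1 − 8.1/18.9, a risk ratio, set against a hazard ratio. The same Kaplan-Meier values imply a hazard ratio of 0.084/0.21 = 0.40, exactly the planned 60%.

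A further objection concerns the remedy. Subjects censored for not meeting the chronic definition are not all cleared. SAP 8.3 records that some may miss the 6-month window while still viremic, and that others may change dominant genotype and remain chronically infected in practice. Coding all of them as competing events would understate chronic incidence. This stands, and it shapes the fix.

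**Conclusion.** The point holds as a descriptive one. The six figures censor events that the SAP elsewhere models as competing, so as cumulative incidence they are too high wherever such events occur. For cleared infections the excess at 18 months is about 0.5 to 1.7 points in placebo and 0.7 to 1.15 points in vaccine. This rests on constant hazards, equal infection rates by arm, efficacy through clearance only, and 17.5 to 27 infections per 100 person-years. The upper rate implies that 13/27 = 48% of placebo infections clear, well above the 20% in Protocol 2.1, so the upper end of the placebo range may be generous. If the vaccine also prevents infection, its own excess is smaller. The figure shells are not reproduced, so it is unknown whether survival or its complement is plotted; the distortion is the same size either way. The primary hazard ratio, confidence interval and p-value are unaffected.

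**What to change.** Replace Figures 3, 4, 7, 8, 11 and 12, or accompany them, with Aalen-Johansen cumulative incidence curves by arm, using the same event codes as the Fine-Gray models. Keep the stratified Cox model as the primary test.

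Set the event codes before unblinding and use one set for both the curves and the Fine-Gray models:
- Figures 3, 4, 7 and 8: only true clearance is the competing event. SAP 3.3.5 already dates clearance by two consecutive undetectable samples.
- Figures 11 and 12: other-genotype chronic infection is the competing event. State how cleared infections are coded, since the SAP does not say.
- Subjects who missed the window, or whose outcome is indeterminate, stay censored. The Fine-Gray wording in SAP 8.1 is broader than this and should be narrowed to match.

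Matching non-1 curves would be a useful extra, because Table 26 reports non-1 infection while Figures 11 and 12 show genotype 1 only.

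The cost is figure code plus one coding decision that the Fine-Gray models need anyway. No new data are required and no alpha is spent.

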 # of Subj = the number of subjects that reported at least one protocol deviation in the category specified.
 # of Dev = the total number of protocol deviations reported for the category specified.

Table 8: Vaccine Efficacy Against 6-Month Chronic HCV Infection by Treatment Group and Analysis Population

Analysis	Population	Number of Chronic HCV Infections				Vaccine Efficacy [1]	95 % CI for Vaccine Efficacy [2]	P-value [3]
		Vaccine		Placebo				
		Number of Subjects n	Total Subjects N	Number of Subjects n	Total Subjects N			
Primary Efficacy Analysis	ATP population	x	x	x	x	x.xx	x.xx, x.xx	0.xxx
Secondary Efficacy Analysis	mITT population	x	x	x	x	x.xx	x.xx, x.xx	0.xxx
Sensitivity Analyses	ATP population – Fine-Gray	x	x	x	x	x.xx	x.xx, x.xx	0.xxx
	mITT population – Fine-Gray	x	x	x	x	x.xx	x.xx, x.xx	0.xxx
	ATP population – Covariate-Adjusted	x	x	x	x	x.xx	x.xx, x.xx	0.xxx
	mITT population – Covariate-Adjusted	x	x	x	x	x.xx	x.xx, x.xx	0.xxx

Note: N = Number of subjects in specific treatment group.
 [1] Vaccine efficacy is obtained from stratified/covariate-adjusted Cox regression.
 [2] 95% CI = 95% confidence interval obtained from stratified/covariate-adjusted Cox regression.
 [3] P-value = p-value from score test comparing treatment groups obtained from Cox regression (log-rank for Primary and Secondary analyses).

Table 9: Stratum-Specific Vaccine Efficacy Against 6-Month Chronic HCV Infection by Treatment Group and Analysis Population

Analysis Population		Number of Chronic HCV Infections				Vaccine Efficacy [1]	95 % CI for Vaccine Efficacy [2]	P-value [3]
		Vaccine		Placebo				
		Number of Subjects n	Total Subjects N	Number of Subjects n	Total Subjects N			
ATP	All subjects	x	x	x	x	x.xx	x.xx, x.xx	0.xxx
	Males	x	x	x	x	x.xx	x.xx, x.xx	0.xxx
	Females	x	x	x	x	x.xx	x.xx, x.xx	0.xxx
	CC	x	x	x	x	x.xx	x.xx, x.xx	0.xxx
	CT/TT	x	x	x	x	x.xx	x.xx, x.xx	0.xxx
mITT	All subjects	x	x	x	x	x.xx	x.xx, x.xx	0.xxx
	Males	x	x	x	x	x.xx	x.xx, x.xx	0.xxx
	Females	x	x	x	x	x.xx	x.xx, x.xx	0.xxx
	CC	x	x	x	x	x.xx	x.xx, x.xx	0.xxx
	CT/TT	x	x	x	x	x.xx	x.xx, x.xx	0.xxx
ATP- Fine-Gray	All subjects	x	x	x	x	x.xx	x.xx, x.xx	0.xxx
	Males	x	x	x	x	x.xx	x.xx, x.xx	0.xxx
	Females	x	x	x	x	x.xx	x.xx, x.xx	0.xxx
	CC	x	x	x	x	x.xx	x.xx, x.xx	0.xxx
	CT/TT	x	x	x	x	x.xx	x.xx, x.xx	0.xxx
mITT -Fine Gray	All subjects	x	x	x	x	x.xx	x.xx, x.xx	0.xxx
	Males	x	x	x	x	x.xx	x.xx, x.xx	0.xxx
	Females	x	x	x	x	x.xx	x.xx, x.xx	0.xxx
	CC	x	x	x	x	x.xx	x.xx, x.xx	0.xxx
	CT/TT	x	x	x	x	x.xx	x.xx, x.xx	0.xxx

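### SAP 8.1 and 8.3 define the IL28B-by-time interaction with the gender indicator, contradicting the code beside it; the covariate-adjusted code also requests no treatment score test

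*SAP*

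**What the plan says.** SAP 8.1 plans a sensitivity analysis in which gender and IL28B status become fixed effects instead of stratification factors. It first defines a gender-by-time term from the gender indicator. It then says that "the interaction between time and IL28B status will be assessed using the product of time and the binary indicator for gender". The same sentence appears in SAP 8.3 for Objective 1, covering both the standard and the interval-censored Cox models.

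The pseudocode beside this text reads "model time*status(0) = treatment gender|time il28bstatus|time", which uses the IL28B variable. The unstratified Fine-Gray code in 8.1 and both adjusted models in 8.3 Objective 1 do the same.

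On the p-value, SAP 8.1 states of the adjusted model: "The p-value from the score test of the treatment main effect will be calculated and presented". Footnote [3] of the Table 8 shell describes a "p-value from score test comparing treatment groups obtained from Cox regression" and reserves the log-rank label for the primary and secondary rows. The Table 14 shell (9-month chronicity) has the same rows and an equivalent footnote. The code's output line keeps only the hazard ratio and its confidence limits.

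**The concern.** The stated rule for IL28B-by-time says nothing about IL28B. IL28B is a randomization factor and a stratum in the primary model. The sensitivity model replaces that stratification with a proportional effect, so a check of IL28B proportionality is relevant there, and the prose does not provide one. SAP section 1 requires deviations from the SAP to be described and justified in the clinical study report. As written, following the text departs from the code, and following the code departs from the text.

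The score-test gap is smaller. In the primary model treatment is the only covariate, so the overall score test is the stratified log-rank test, as 8.1 says. Once gender, IL28B and time products are added, the overall test and the treatment test differ. The code requests nothing that yields the treatment test, so the p-value cells for the covariate-adjusted rows of Tables 8 and 14 have a correct description but no specified source.

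**Working it through.** **1. The interaction term.** Let x, g and c be the vaccine, female and CC indicators.

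- Prose: log h(t) = a(t) + βx + γg + δc + θ₁·t·g + θ₂·t·g. Only θ₁ + θ₂ is identifiable. The information matrix, evaluated on simulated data, has rank 4 of 5.
- IL28B indicator: log h(t) = a(t) + βx + γg + δc + θ₁·t·g + θ₂·t·c. The rank is 5 of 5, and θ₂ is the intended parameter.
- If the two products were instead examined in separate models, the second would simply repeat the gender test.

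**2. The plan's own figure.** SAP section 5 plans on 43 ATP events, 85% power and a hazard ratio of 0.40. The test it names is a "two-sided log rank test conducted at the significance level (alpha) of 0.05".

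- Schoenfeld events: 4 × (1.960 + 1.036)² / ln(0.4)² = 4 × 8.98 / 0.840 = 42.8, so 43. Power at 43 events is 85.2%.
- Expected events, using "Assuming 14 cases/100 person-years (PY) in the control group, and 5.6 cases/100 PY in the vaccine group" with 292.5 subjects and 1.5 years: 292.5 × 1.5 × (0.14 + 0.056)/2 = 43.0.

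Both figures reproduce.

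**3. Power if a joint score test were read as the treatment test.** With covariates that have no effect, the noncentrality is 43 × 0.25 × ln(0.4)² = 9.03 whatever the degrees of freedom.

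| df | Terms | Power |
|---|---|---|
| 1 | treatment | 85% |
| 3 | plus gender, IL28B | 71% |
| 5 | plus two time products | 63% |
| 6 | the six terms the code expands to | 59% |

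**4. Rejection with an inert vaccine.** This is a simulation of 1,000 replicates per scenario with 292 subjects. Hazards are scaled so that mean hazard × 1.5 years × 292 = 43. The assumptions, none from the documents, are 30% female, 40% CC, exponential times, light random censoring, and the hazard ratios (HRs) shown.

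| Female HR, CC HR | Treatment-only score test | Joint 3 df | Joint 5 df (true time-dependent products) |
|---|---|---|---|
| 1, 1 | 5.3% | 5.6% | 4.7% |
| 1.5, 0.6 | 4.5% | 31% | 25% |
| 2.0, 0.4 | 4.5% | 79% | 72% |

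A separate 3-df simulation at (14 + 5.6)/2 = 9.8 events per 100 person-years, with 292 or 351 subjects, gave 10% with CC HR 0.75 alone and 48–55% with CC HR 0.5 and female HR 1.5. The direction is stable; the size depends on the assumed covariate effects.

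**5. How `time` enters.** The bar notation expands to treatment, gender, time, gender×time, IL28B and IL28B×time. No programming statement makes `time` time-dependent. Read literally, each subject's own follow-up time becomes an ordinary covariate. At each event the failing subject has the smallest value in the risk set, so the likelihood keeps rising as the coefficient falls. In a trial fit the coefficient had passed −2,500 after 12 Newton steps and was still falling. The 6-df joint test rejected in every replicate, including those with no effect of anything. Correcting the indicator name and requesting a treatment score test would therefore not be enough without this change.

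**The case against.** The best defence is that this is a copying slip. The sentence names IL28B as its subject, and every matching MODEL statement uses the IL28B variable. That largely stands. A reader might infer that the fitted test would use gender and so have little power for IL28B. The documents do not support this: no code in the SAP runs such a model, and the literal prose gives no IL28B test at all, not a weak one. What remains is a wrong rule in a methods section that conflicts with its own code.

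On the score test, the text and the footnotes already name the right null. A reader might infer that the covariate-adjusted p-value in Table 8 would be a joint test and could be significant with an inert vaccine. That requires a programmer to disregard the explicit wording. The code is labelled pseudocode and saves no p-value even for the primary model, so it cannot be taken as the p-value specification. Which score test the software prints by default is not stated in the documents, and the point does not depend on it.

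The interaction estimates go only to report text and drive no decision rule. SAP section 8 also provides for residual and other diagnostic plots. Both limit the consequence.

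**Conclusion.** The point holds as a text error with an accompanying code alignment. The prose in 8.1 and 8.3 Objective 1 specifies no test of IL28B-by-time and contradicts the adjacent code; this follows from the wording alone. The treatment score test is correctly promised, but the pseudocode does not request it.

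The scope is the covariate-adjusted Cox models, including the 9-month version, which follows 8.1, and the Objective 1 adjusted models. The `time` problem also reaches the unstratified Fine-Gray model. The primary stratified Cox and log-rank analysis is unaffected: it has treatment as its only covariate and a separate baseline hazard for each gender-by-IL28B stratum, so it does not need IL28B proportionality.

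The power losses in step 3 follow from the plan's own inputs, but apply only if a joint test were misread as the treatment test. The rejection rates in step 4 also rest on assumed covariate hazard ratios and frequencies. They show why the source of the p-value should be stated; they do not predict what this trial would report. The priority is low, but the correction is almost free.

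**What to change.** Make these changes together, before unblinding:

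1. In SAP 8.1 and 8.3 Objective 1, change the second product to *time and the binary indicator for IL28B status (CC vs CT/TT)*.
2. In the covariate-adjusted Cox code, request an effect-level score test, for example with `TYPE3(SCORE)`. State that the covariate-adjusted p-values in Tables 8 and 14 come from the 1-df treatment row. If a Wald p-value is preferred, say so and change the footnotes. Apply the same rule to any p-value reported from the Objective 1 adjusted models.
3. Define the gender and IL28B time interactions as time-dependent covariates and drop the `time` main effect wherever the bar notation appears.

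The cost is two wording changes, one code option, and a rewrite of the interaction terms in the pseudocode. No new data and no change to the primary analysis are needed.
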